#### 2. - SYNOPSIS

# 2.1 Type of request

Single-centre clinical trial with an active principle of a pharmaceutical specialty already marketed in Spain to be used as an adjuvant in the treatment of schizophrenia in the early stages of the disease Vs other pharmaceutical specialties authorized as routine clinical use.

Coordination Centre: UGC Salud Mental- Clinical Trials Unit (UICEC-HUVR).

#### 2.3 Protocol Title:

Cognitive effects of adyuvant vortioxetine in early schizophrenia

#### 2.4 Protocol Code:

**CAVES** 

EudraCT Number: 2021-001333-38

#### 2.7 Ethical committee for clinical research

Reference committee: Provincial CEIm of Seville.

#### 2.9 Study intervention:

Each patient will be treated with each of the study arms, due to the cross-over design; so every of the 37 foreseen patients to be included will be acting as autocontrol receiving both, experimental and control arm with a 2-week wash out period between the 2 phases of the study.

#### Experimental treatment: Vortioxetine.

Dose: Vortioxetine will be started at 10 mg / day for 2 weeks, followed by 20 mg / day for the remainder of the study. The vortioxetine dose may be reduced to 5 mg or 10 mg for reasons of tolerability at the discretion of the physician.

Control treatment: TAU (Treatment as usual)

As TAU, any medication, routine support or referral to other services, which are deemed medically appropriate, is allowed.

A 2-week washout phase will be required from week 24 to week 26 and at the end of the study (week 50 to week 52).

The two trial periods in which the patient receives the different treatments whose effects are being compared should be separated by a washout phase that is

sufficient to rule out any carry-over effects. In other words, the effect of the first treatment must have completely worn off before the starting of the second period.

The first trial period will last for 24 weeks, then a two-week washout period, and the second trial period will last for 24 weeks, with a two-week washout period at the end of the trial.

The total trial time will last 52 weeks.

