The two trial periods in which the patient receives the different treatments whose effects are being compared should be separated by a wash-out phase long enough to rule out any carry-over effects. In other words, the effect of the first treatment must have completely worn off before the start of the second period. With vortioxetine that period is 2 weeks.

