#### 6.- STUDY DESIGN

## 6.1 Endpoints

## 6.1.1 Principal endpoint

The primary endpoint of the response consists of the improvement in cognitive functioning as assessed by the change in the BACS App Scale score: changes from baseline to week 24 (and from week 26 to week 50 in the 2nd period) in the scores of the BACS App Scale, using the Composite Z Score defined as the weighted sum of the patient's Individual Z Score (frame time: baseline visit, week 24, week 26 and week 50).

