#### 6.5 Follow-up

The follow-up of the patients will be carried out in the visits defined in this protocol. After signing the informed consent, patients will undergo a screening visit to confirm their eligibility for the study. If all the inclusion and exclusion criteria are correct, patients will undergo an initial evaluation and then will be randomized 1: 1 to 24 weeks of adjuvant treatment with vortioxetine or TAU.

Thereafter, patients will be seen in week 1, 4 and monthly for the next 5 months. At the end of this period, having reached week 24, the patient will undergo a washout

period of two weeks (regardless of the assigned arm) to ensure that in the case of starting the trial in the experimental arm, there will be no effect. carry-over caused by vortioxetine at the start of the second period (week 26)

There are 2 wash weeks that will take place between the two test periods (week 24 to week 26), and a second wash that will take place at the end of the second period (week 50 to week 52) (figure 1).

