#### CAVES PROTOCOL CONFIDENTIAL VERSION 1.0

Hematology/Chemistry 		Х							Х
Dispense Treatment 11		Х	Х	Х	Х	Х	Х	Х	
Compliance 12			Х	Х	Х	Х	Х	Х	Х
Concomitant Medication	X	Х	Х	Х	Х	Х	Х	Х	Х
Adverse Events			Х	Х	Х	Х	Х	Х	Х

- 1. Between week 24 and week 26 the first wash period takes place. The washing time between one period and another will be 2 weeks
- 2. HAMD-17: Hamilton Rating Scale for Depression
- 3. BARS: Behaviorally Anchored Rating Scale
- 4. PANSS: Positive and Negative Syndrome Scale
- 5. SAS: Sedation-Agitation Scale
- 6. SANS: Scale for Assessment of Negative Symptoms
- 7. BACS: Brief Assessment of Cognition in Schizophrenia
- 8. BACS App: Brief Assessment of Cognition in Schizophrenia App. Versión de la Escala BACS en aplicación para Tablets: facilitará la realización de pruebas repetidas y reducirá efectos de la práctica. Existen diferentes versiones de la prueba.
- 9. NSA-4: Negative Symptom Assessment (4-Item)
- 10. GAF: Global Functionality Assessment Scale
- 11. Vortioxetine dosage according to Summary of Product Characteristics (section 6.5 of protocol)
- 12. Patient must bring test medication at each visit for counting. Empty boxes will stay in the center
- 13. Complete blood count including leukocyte, neutrophil, hemoglobin, and platelet counts. Blood chemistry that includes the determination of sodium, potassium, creatinine, urea, lipid profile, glycemia.

CAVES PROTOCOL CONFIDENTIAL VERSION 1.0

Procedures PERIOD 2	Visit10 (Day 183±3) Week 26	Visit11 (Day 190±3) Week 27	Visit12 (Day 211±3) Week 30	Visit13 (Day 239±3) Week 34	Visit14 (Day 267±3) Week 38	Visit15 (Day 295±3) Week 42	Visit16 (Day 323±3) Week 46	Visit17 (Day 351±3) Week 50 	Visit18 (Day 379±3) Week 52
Pregnancy Test	Х								X
Medical History	Х	Х	Х	X	Х	Х	Х	Х	X
HAMD-17	Х								
BARS	Х								
PANSS	Х							Х	Х
SAS	Х	Х	X	X	Х	Х	Х	Х	
SANS	X		X		Х			Х	
BACS	X				Х			X	Х
BACS App	X							X	
NSA-4	X		X		Х			X	
GAF	X				Х			X	Х
Vitals Signs: weigth, Height, Blood Pressure, Pulse Rate, abdominal perimeter	х		х		Х			х	Х
Hematology/Chemistry	X							X	Х
Dispense Treatment	X	Х	X	Х	Х	X	X		
Compliance		Х	X	Х	Х	Х	X	X	
Concomitant Medication	X	Х	X	Х	Х	X	X	X	Х
Adverse Events	X	X	X	X	Х	X	X	X	X

1. Between week 50 and week 52 the second wash period takes place. The visit corresponding to week 52 corresponds to the FINAL VISIT OF THE TRIAL.

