# 9.1 Procedures per visit

The follow-up of the patients in the present study consists of 9 scheduled visits in each period (18 in total). Depending on which arm the patient falls on, the trial treatment will begin in one period or another. That is, if after the randomization of the patient, he falls into the Experimental Arm, the treatment will begin on Visit 2 (Day 1) and will end in week 24, corresponding to period 2 as the TAU treatment period. If, on the other hand, the patient falls into Control Arm, the study will begin with a first TAU period (continues with the treatment according to clinical criteria) and it will be in period 2 when the trial treatment begins (in week 26 of the study).

In this protocol the visits are arranged in chronological order, specifying the week to which each one corresponds.

The following sections detail the procedures that must be carried out at each visit.

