# 9.1.9 Visit 9: End of Treatment Visit (Week 24: day 169 ± 3 days)

- Physical examination: weight, blood pressure, heart rate, respiratory rate, temperature and abdominal perimeter
- Clinical, cognitive and functional evaluation: SAS, SANS, BACS, PANSS, GAF and NSA-4
- Dosing and dispensing treatment
- Adherence to treatment
- Review of concomitant medication
- Review of adverse events

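### The Visit 9 and Visit 10 windows allow 8 to 20 days between visits, so a gap can meet both windows and still break the protocol's own 2-week washout before the week-26 primary baseline

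*Protocol*

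**What the plan says.** Section 2.9 calls for a 2-week washout between weeks 24 and 26 and gives its purpose: "the effect of the first treatment must have completely worn off before the starting of the second period". Section 4 repeats the principle and fixes the time: "With vortioxetine that period is 2 weeks". Section 6.5 says the washout is there to prevent "carry-over caused by vortioxetine at the start of the second period (week 26"). Footnote 1 of the section 9 schedule restates the duration: "The washing time between one period and another will be 2 weeks".

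The primary endpoint in section 6.1.1 uses week 26 as a baseline: "changes from baseline to week 24 (and from week 26 to week 50 in the 2nd period").

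For the vortioxetine-first sequence, section 9.1 says "the treatment will begin on Visit 2 (Day 1) and will end in week 24". Section 9.1.9 names Visit 9 the "End of Treatment Visit (Week 24: day 169 ± 3 days"), and section 9.1.10 puts Visit 10 at day 183 ± 3. Day 1 is Visit 2. No section sets a minimum number of days between Visits 9 and 10, or counts Visit 10 from the last dose.

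The Visit 9 list in section 9.1.9 also includes "Dosing and dispensing treatment". The schedule table marks no dispensing at week 24. The parallel week-50 list (section 9.1.17) has no dispensing and starts the washout instead.

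**The concern.** The protocol states how long vortioxetine needs to wear off, then gives visit windows that do not secure that time. The nominal schedule has no slack: the planned gap equals the required gap. Any delay at Visit 9 that is not matched at Visit 10 therefore brings the washout below 2 weeks.

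The week-26 BACS App score is the starting point for the period-2 change. In a vortioxetine-first patient that change is the TAU change. If some benefit is still present at week 26 and then fades, the fading is scored as worsening on TAU, and the vortioxetine-minus-TAU difference becomes too large. Control-first patients have no vortioxetine to clear at week 26 and are not exposed.

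The dispensing line in section 9.1.9 adds to the uncertainty, because it hands out treatment on the day the washout should start.

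**Working it through.** **Inputs (protocol).** Visit 9: day 169 ± 3, so days 166 to 172. Visit 10: day 183 ± 3, so days 180 to 186. Visit 11: day 190 ± 3, so from day 187. Required washout: 14 days.

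**The plan's own figure.** Nominal gap = 183 − 169 = 14 days, which reproduces the stated 2 weeks.

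**What the windows allow.**
- Shortest gap: 180 − 172 = 8 days.
- Longest gap: 186 − 166 = 20 days.
- If dosing stops on day 169 whatever the visit date: 180 − 169 = 11 to 186 − 169 = 17 drug-free days.
- Of the 7 × 7 = 49 permitted day pairs, 6 + 5 + 4 + 3 + 2 + 1 = 21 fall short of 14 days, by 1, 2, 3, 4, 5 and 6 days respectively. The mean shortfall among them is (6 + 10 + 12 + 12 + 10 + 6)/21 = 56/21 = 2.67 days. The 8-day gap is 1 pair of 49.

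**Direction of the bias.** Let d be the true effect and ρ the fraction of it left at week 26, gone by week 50. Leave aside period and practice effects.
- Vortioxetine-first: change on vortioxetine is d and change on TAU is −ρd, so the difference is d + ρd.
- Control-first: the difference is d.

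With half the patients in each sequence, the mean is d(1 + mean ρ/2), where mean ρ is taken over vortioxetine-first patients. If d = 0, the bias is 0 for every ρ.

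**Size, by assumption only.** The protocol gives neither a value for ρ nor a distribution of visit dates. Suppose the two visit days fall independently and evenly over their windows, dosing continues to Visit 9, and the residual falls linearly from r at 8 days to 0 at 14 days. Then mean ρ = (21/49) × (2.67/6) × r = 0.190r, and the overstatement is 0.095r.

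| r at 8 days | Overstatement | True 0.5 estimated as |
|---|---|---|
| 0.1 | 1.0% | 0.505 |
| 0.25 | 2.4% | 0.512 |
| 0.5 | 4.8% | 0.524 |

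For scale, take the SD of 1 in section 12.1 as that of the within-patient difference, with 37 × 0.85 ≈ 31 completers. The standard error is then 1/√31 ≈ 0.18, and the largest shift in the table, 0.024, is about 0.13 of it.

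**Feasibility of a 14-day minimum.** 166 + 14 = 180 and 172 + 14 = 186, so every permitted Visit 9 date leaves at least one permitted Visit 10 date. The latest Visit 10, day 186, precedes the earliest Visit 11, day 187. Of the 49 pairs, 28 remain, with gaps of 14 to 20 days.

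**The case against.** The strongest reply is that the 2-week washout is a requirement in its own right, stated in sections 2.9 and 8.1 and in footnote 1. A site leaving 8 days would break it, and a site that follows the footnote would book Visit 10 from the actual Visit 9 date. This stands. A reader might infer that an 8-day gap is fully protocol-compliant; it is not. It satisfies the windows and fails the footnote. What remains is a conflict: a check of visit windows would pass a gap that a check of the washout would fail.

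Second, 21 of 49 is a count of permitted pairs and not a forecast. Linked booking would make short gaps rarer, and the windows do not force any. This also stands.

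Third, a reader might infer a larger bias by letting the full fraction r persist at every gap below 14 days and vanish at day 14. That gives 0.429 × r/2, or 2%, 5% and 11% for r = 0.1, 0.25 and 0.5. It needs the residual effect to disappear between days 13 and 14, which nothing in the protocol supports.

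Fourth, the dispensing line repeats the wording of the earlier visit lists and looks like an editorial slip. That is likely, but it is still a wrong instruction at the visit where it matters. Section 4 mentions a recommended week at 10 mg before stopping from 15 mg or more. A reader might infer that the Visit 9 supply is for that week, leaving 7 drug-free days. The protocol does not prescribe this.

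Finally, a discontinuation effect at week 26 would act in the opposite direction, and the period-1 comparison in section 12.2 is untouched.

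**Conclusion.** The point holds as a conflict between the protocol's washout requirement and its visit windows, made worse by the dispensing entry in section 9.1.9. The 8-to-20-day and 11-to-17-day ranges are exact arithmetic on the stated days.

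The consequence is limited. Only vortioxetine-first patients are exposed, and bias towards vortioxetine requires a true effect that is still partly present at week 26. With no true effect there is no bias, so inflation of the type I error from this source is not supported. The size cannot be computed from the protocol; the percentages shown are illustrations under stated assumptions, and the effect is probably small. The sample size is unaffected. The change is worth making because it protects a primary baseline at almost no cost.

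**What to change.** 1. Keep days 180 to 186 for Visit 10 and add one condition: at least 14 days after the last vortioxetine dose, or at least 14 days after Visit 9 in control-first patients.
2. State that the last vortioxetine dose is taken at Visit 9, after the week-24 assessments.
3. Delete the dosing and dispensing line from section 9.1.9.
4. Record the date of the last dose in the case report form.

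Do not require a step-down to be completed before Visit 9. That would lower the dose just before the week-24 primary assessment.

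The cost is two added sentences, one deleted line and one data field, with no extra visits, weeks or patients. There are two downsides. Booking of Visit 10 becomes less flexible, from 7 permitted days when Visit 9 is on day 166 to 1 when it is on day 172. Patients on 20 mg would also stop without the recommended week at 10 mg; section 4 says abrupt stopping is possible.

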# 2.10 Study products

Financing and supply of study products: H. Lundbeck A/S

Product: vortioxetine

Trademark: Brintellix®

Pharmaceutical Form: tablets

Administration way: Oral

Therapeutic Group: Psychoanaleptics; Other antidepressants

Quantitative and qualitative composition of the product: the product is presented in doses of 5, 10 and 20 mg / tablet. Each carton contains 25 blisters with 10 tablets per blister.

According to product data sheet (about protocol, period of treatment is 24 weeks):

- first 2 weeks: 10 mg/day → 14 tablets/patient of 10mg
- next 22 weeks: 20 mg/day → 308 tablets/patient of 10mg
- 322 tablets/patient/10mg + 10% → 355 tablets/patient/10 mg
- as each box of Brintellix contains 250 tablets → 2 box of 10 mg/patient

TOTAL: 2 box of 10mg/ patient x 37 patients  $\rightarrow$  74 box of 10 mg and 15 box of 5 mg.

Treatment control: usual antipsychotic treatment (TAU)

As TAU, any medication, routine support or referral to other services, which are deemed medically appropriate, is allowed. The only limitations are to refrain from:

- 1. Refer patients for Cognitive Behavioural Therapy (CBT) or other brief cognitive therapies unless absolutely necessary.
- 2. Adding other cognitive enhancers. Antidepressant medication as a routine part of routine treatment is not restricted.
- 3. ECT (Electroconvulsive Therapy) may not be prescribed for the duration of the trial.

# 2.11 Clinical trial phase

Phase IIb/III

# 2.12 Objectives

Principal objective: evaluate the efficacy of vortioxetine against TAU in the treatment of cognitive impairment in newly diagnosed schizophrenia, measured by the change from baseline to week 24 (and from week 26 to week 50 in the 2nd period) in the BACS App Scale scores, using the Composite Z Score defined as the weighted sum of the patient's Individual Z Score (frame time: baseline visit, week 24, week 26 and week 50).

Secondary objective: to evaluate the efficacy of vortioxetine against TAU in the treatment of negative symptoms in newly diagnosed schizophrenia, measured by the change in the severity of negative symptoms (SANS total scores, NSA-4) from baseline. until completion (frame time: baseline visit, week 4, week 12, week 24, week 26, week 30, week 38 and week 50).

Additionally the following secondary objectives will be evaluated To assess
the efficacy of vortioxetine versus TAU in the treatment of cognitive deficits in
newly diagnosed schizophrenia, as measured by change in general
functioning (GAF total score) (frame time: baseline visit, week 12, week 24,
week 26, week 38 and week 50)

Evaluate the safety of vortioxetine in patients with newly diagnosed schizophrenia measured through the communication of any serious adverse event evaluated in relation to the Experimental Treatment (frame time: from consent signature to week 52).

 Evaluate the efficacy and reliability of the BACS App Vs BACS, measured by performing both scales and comparing results. The purpose is to confirm the reliability of the results when performing the BACS App as a faster and more practical model at the beginning and end of each period (Measurement time: baseline visit, week 24, week 26 and week 50) compared to the results obtained with the BACS scale performed at each trial visit (Measurement time: from consent signature to week 52).

# 2.13 Study design:

Open-label, randomized, crossover, single-centre clinical trial IIb / III to evaluate the efficacy of vortioxetine compared to standard treatment in recently diagnosed schizophrenia.

[figure not shown]

Figure 1

This is a 12-month (52-week), randomized, crossover study comparing vortioxetine as adjunctive treatment in 37 stabilized patients (25 per arm) in early stages of the disease (less than 3 years from first treatment. stable antipsychotic) with a diagnosis of schizophrenia spectrum disorder determined by the structured DSM-5 clinical interview (SCID).

Subjects who drop out of the trial before its completion will not be replaced.

# 2.14 Study indication

Recently diagnosed schizophrenia.

In the literature there is a great diversity of definitions that describe the period called "early course" of schizophrenia. Given the lack of consensual and standardized definitions, a recent review was made, reaching the conclusion that the definitions that use the duration criterion for the definition of schizophrenia of recent onset, use a range of cut-off points ranging from 1 month up to 10 years, with 1, 2 and 5 years being the most frequent. Based on this review, the 3-year inclusion criterion is adjusted to the current literature in the field of early schizophrenia.

# 2.15 Primary endpoint

To assess the effectiveness of Vortioxetine vs. TAU measured by the change in Brief Assessment of Cognition in Schizophrenia (BACS App) scores

# 2.16 Study population and number of planned subjects.

Patients in the early stage of the disease (less than 3 years from the first stable antipsychotic treatment) with a diagnosis of schizophrenia disorder determined by the DSM-5 Structured Clinical Interview (SCID).

50 patients will be recruited from the area covered by the Virgen del Rocío University Hospital (whose population is 800,000 people). Outpatients will be evaluated for inclusion and exclusion criteria.

Patients with a clinical stability of at least 3 months, with stable treatment of antipsychotics and psychotropic medications for at least the last 4 weeks. Patients without depression diagnosis, positive psychotic symptoms (PANSS) or extrapyramidal EPS symptoms (SAS, BARS) will be eligible.

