# 6.3 Randomization procedure

Patients will be recruited within the health area corresponding to the center participating in the trial, the Virgen del Rocío University Hospital in Seville. They will be detected from institutionalized patients who attend the mental health network devices on an outpatient basis.

In those patients with a diagnosis of early evolution Schizophrenia with a stable treatment with antipsychotics for at least 4 weeks, the inclusion and exclusion criteria of the study will be verified, and informed consent will be requested after completing the ACE questionnaire, to measure the degree capacity of understanding of the person who signs. Patients who meet all the inclusion criteria, but have some exclusion, will be considered screening failure, and the reason for exclusion should be collected. Subjects who drop out of the trial before the end of the trial will not be replaced.

Once the informed consent has been signed, randomization will be carried out, which will be centralized online, in a 1: 1 ratio (adjuvant treatment with vortioxetine vs treatment in usual clinical practice).

The randomization system will be available online in the CRDe (Electronic Data Collection Notebook) designed for this purpose. The list of assignments will be generated using specific software and will be included in the CRD.

The randomization list will be guarded by the Clinical Trials Unit (UICEC). Once you have entered that you meet all the inclusion criteria and none of the exclusion criteria, the researcher will obtain the assigned treatment and the patient's code, which will be made up of a numerical code that identifies the center and patient (per example: XX-XXX).

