#### 12.- STATISTICS

# 12.1 Sample size calculation

As it is a crossover design, each individual acts as their own control, that is, an initial treatment is assigned and after a while it is changed. Therefore, the correct thing to do would be to calculate the sample under the premise of related or paired samples, for this case it would be the dependent samples T test.

The sample size can be calculated in two ways, in the first one, the difference in the means to be detected of the primary variable (BACS), the standard deviations of the treatment change, and the correlation coefficient must be established; while the second is to consider the difference in the means to be detected for the primary variable (BACS) and the standard difference of the differences.

Accepting an alpha risk of 0.05 and a beta risk of 0.2 in a bilateral contrast, 37 subjects are required to detect a difference equal to or greater than 0.5 units. A standard deviation of 1 is assumed. A loss to follow-up rate of 15% has been estimated.

That is, based on the previous parameters, and using a confidence level of 95% and power of 80%, 37 subjects are needed.

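### The protocol plans for 37 patients in four places and for 50 in two, and the two totals cannot both be the number randomised

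*Protocol*

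**What the plan says.** Four sections give 37:

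- Section 2.9 on the crossover: "so every of the 37 foreseen patients to be included will be acting as autocontrol".
- Section 2.10 on drug supply: "2 box of 10mg/ patient x 37 patients", which comes to 74 boxes of 10 mg.
- Section 2.13 on the design, in its leading figure: "37 stabilized patients (25 per arm".
- Section 12.1 on sample size: "37 subjects are required to detect a difference equal to or greater than 0.5 units. A standard deviation of 1 is assumed".

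Two places point to 50:

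- Section 2.16, on the study population and planned number: "50 patients will be recruited from the area covered by" the hospital.
- The bracket in the same phrase of section 2.13, which puts 25 patients in each arm. Section 6.3 randomises "in a 1: 1 ratio (adjuvant treatment with vortioxetine vs treatment in usual clinical practice", so 25 per arm is 50 in total.

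Section 12.1 also states "Accepting an alpha risk of 0.05 and a beta risk of 0.2 in a bilateral contrast" and "A loss to follow-up rate of 15% has been estimated". Sections 2.13, 6.3 and 6.6 say that dropouts are not replaced.

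**The concern.** The number to be randomised sets the recruitment target, the power and the drug order. Because dropouts are not replaced, it also determines how many completers can be expected. Here the section that is meant to state the number disagrees with the section that calculates it, and the design section contains both figures.

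A trial that stops at 37 would meet section 12.1 and fall 13 patients short of section 2.16. The trial is open-label (section 6.4), so the question of which total applies should not remain open while outcome data accumulate.

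**Working it through.** **Inputs (section 12.1).** Two-sided alpha 0.05, beta 0.2, difference to detect 0.5, SD 1, loss to follow-up 15%, dependent-samples t test.

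**1. Reproducing the plan's 37.** With the SD of 1 taken as the SD of the within-patient difference, the normal approximation is

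n = ((z₀.₉₇₅ + z₀.₈₀) × SD / difference)² = ((1.960 + 0.842) × 1 / 0.5)² = 31.40.

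Allowing for the loss: 31.40 / (1 − 0.15) = 36.94, so 37. The figure reproduces, and the 15% loss is already inside it. Other conventions stay close: rounding up to 32 first gives 32/0.85 = 37.6, so 38, and the exact paired t test needs 34 evaluable patients, 34/0.85 = 40.

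**2. Can 50 come from the same inputs?**

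- Applying the 15% loss to 37 a second time: 37/0.85 = 43.5, so 44.
- Loss needed to go from 31.40 to 50: 1 − 31.40/50 = 37.2%.
- Loss needed to go from 37 to 50: 1 − 37/50 = 26%.

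Neither of the last two rates appears in the protocol.

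**3. Can 25 per arm come from 37?** Under 1:1 allocation, 37 patients split 18 and 19 between the two sequences. Counted by treatment received in the crossover, there are 37 on each treatment. Neither count is 25, whereas 2 × 25 = 50 matches section 2.16.

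**4. Power under each total.** Noncentral t, two-sided 0.05, difference 0.5, SD of the difference 1, 15% loss:

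| Randomised | Expected completers | Power |
|---|---|---|
| 37 | 37 × 0.85 = 31.45 (31 to 32) | 76.8% to 78.2% |
| 50 | 50 × 0.85 = 42.5 (42 to 43) | 88.6% to 89.3% |

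The 80% in section 12.1 is the normal-approximation figure for 37. The named t test gives 2 to 3 points less.

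**5. Drug supply (section 2.10).** At two 10 mg boxes per patient, 2 × 37 = 74, as printed, and 2 × 50 = 100. If boxes may be split between patients, 74 × 250 = 18,500 tablets, which covers 50 × 355 = 17,750.

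**6. Which SD?** Section 12.1 describes two routes: one uses the SDs with a correlation, the other the SD of the differences. It gives no correlation, and it does not say which SD equals 1. The second route returns 37. The first would return it only at a correlation of 0.5, which also makes the SD of the difference 1. If 1 were the SD in each period, assumed correlations of 0.25 and 0.75 would need about 57 and 19 patients after the loss.

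**The case against.** The strongest defence is that 50 counts patients entering assessment and 37 those randomised. Section 2.16 goes on to say that outpatients will be checked against the eligibility criteria, and section 6.3 also speaks of recruiting before it describes that check. This is a fair reading of section 2.16 alone. It does not explain section 2.13, because arms exist only after randomisation and 25 per arm therefore cannot be a screening count. No sentence in the protocol calls 50 a screening figure.

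It can also be said that 37 clearly predominates: it is derived, it appears in four sections and it drives the drug order. That is right. It makes the likely correction editorial, but it does not remove the contradiction.

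Two consequences are modest. Neither total leaves the trial badly underpowered on the stated assumptions, and sizing by the normal approximation is common practice. The 100-box figure applies only if whole boxes are reserved for each patient; with split boxes the 74 would suffice for 50.

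**Conclusion.** The contradiction is real. The protocol gives two totals that differ by 13 patients (35% of 37), and section 2.13 contradicts itself within one phrase. The 37 follows from the stated inputs with the loss already included. The 50 follows from none of the conventions tried, which give 37 to 40, or 44 if the loss is counted twice.

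Power is about 77 to 78% with 37 randomised and about 89% with 50. Both figures assume a within-patient difference with SD 1, a true difference of 0.5 and exactly 15% loss. The shortfall of 2 to 3 points below 80%, and the missing label on the SD, are minor beside the conflict over the total. That 50 and 25 per arm are remnants of another design is plausible but cannot be shown from the document.

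**What to change.** State one number to be randomised, the same in sections 2.9, 2.10, 2.13, 2.16 and 12.1.

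- **If 37 is kept**, as the calculation and the supply figure support: delete the per-arm figure in 2.13 or replace it with 18 or 19 per sequence. In 2.16, correct the 50 or say what it counts, for example patients screened. This costs wording only.
- **If 50 is intended**: add its derivation to 12.1 (power about 89% on the present assumptions) and revise 2.10. This costs 13 more patients and, at two boxes each, 26 more boxes of 10 mg; the 5 mg supply would also need checking.

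In either case, section 12.1 should say which SD the value of 1 refers to; the calculation works if it is the SD of the within-patient difference. As a minor addition, it could note that 37 randomised with 15% loss gives about 77 to 78% power under the paired t test it names.
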